4.1.5 Controlling for Contamination

Access to interventions will be restricted to those assigned to each intervention arm, via the provision of unique access links (Arm 1: Dialogue-Based Webinar) and unique user logins (Arm 2: Social Media Website). To audit for inadvertent contamination across arms, we will monitor who registers for and accesses each intervention on a weekly basis, removing those without legitimate access. During data cleaning we will review participants who may have been exposed to content from more than one trial arm, and make decisions about the removal of these data to control for the influence of contamination.

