4.4.2 Development

The overall designs of the dialogue-based webinar and social media website interventions were informed by prior studies^{22,23,26} and developed using participatory research approaches^{40,41}. In developing content for each intervention, our goal was to maximize consistency of major topics across interventions, in order to isolate effects of each intervention delivery method.

To inform the intervention content, we initially derived topics from several sources, including social media monitoring, news surveillance, online public opinion polls^{42,43}, and peer-reviewed literature³⁹. The major topics for inclusion in both interventions were then refined via interviews with our LTCW partners as part of Aim 3. Additional information was gathered to inform the development of the social media website intervention, the details of which are published

elsewhere⁴⁴. The final list of major topics includes COVID-19 in general, vaccine benefits, vaccine risks, and vaccine development⁴⁴.

We also developed community standards to ensure all participants felt welcome and comfortable when engaging with the interventions. These standards, which are similar across both interventions, were based on the rules of existing vaccine discussion forums and were co-created with our LTCW partners⁴⁴. Also included in both interventions is a video that we developed featuring LTC residents voicing their views on why it is important for LTCWs to be vaccinated.

In response to low intervention exposure in one trial arm (webinar attendance) experienced in the first several weeks of data collection, we developed intervention ‘refreshers’ for each trial arm. The refreshers for trial arms 1 and 2 are briefer, modified versions of each primary intervention. They include content on new and emerging COVID-19 and vaccine-related topics, as well as popular questions trial participants have voiced through their primary intervention engagement. New and emerging topics were derived from several sources, including social media monitoring, news surveillance, online public opinion polls⁴⁵, and consultation with our LTCW partners and other stakeholders. Topics for inclusion were refined primarily via a poll to identify stakeholders’ information needs (process adapted from⁴⁶). Refreshers for trial arms 1 and 2 will be updated as required when there is sufficient new and emerging COVID-19 related public discourse.

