4.7.3 Allocation of Interventions

We will use the randomizer function built into the online Qualtrics survey platform to allocate participants to a trial arm and associated intervention. At the very end of the T0 Survey, the Qualtrics survey platform will automatically generate participants' trial arm and they will be presented with basic information pertaining to their assigned intervention at that time. A 1:1:1 allocation ratio will be used. After submitting their survey, those randomized to Arm 1 (Dialogue-Based Webinar) will be automatically redirected to a separate Qualtrics survey where they can sign up for one of several pre-scheduled webinar sessions. Those randomized to Arm 2 (Social Media Website) will be automatically redirected to the Social Media Website. In order

to access website content, they will first be required to create a username and password for the site. Those randomized to Arm 3 (Enhanced Usual Practice) will be automatically redirected to a specific page(s) on the CDC website (<https://www.cdc.gov/coronavirus/2019-ncov/vaccines/index.html>).

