4.8 Statistical Analysis

4.8.1 Data Source Accuracy

Initial examination of data will include descriptive statistics and frequency distributions in order to check planned analysis assumptions, identify missing data, and check data source adequacy. This process will also inform any necessary variable re-coding prior to data analysis.

4.8.2 Analyses Corresponding to Trial Aims 1 and 2

All analyses pertaining to study Aims 1 and 2 will be conducted on an intention-to-treat (ITT) basis (i.e. the arm participants were assigned to) and as-treated basis (i.e. whether they engaged with their assigned intervention or control). A detailed data analysis methodology, including planned statistical tests, timepoints for outcome assessment, and treatment of missing data, is included in Appendix B.

For Aim 1, hypothesis 1.1, we will conduct one-tailed tests (superiority analysis) to compare the impact of each of the two intervention arms against the enhanced usual practice arm on primary and secondary outcomes. For Aim 1, hypothesis 1.2, we will conduct a two-tailed test (equivalence analysis) of primary and secondary outcomes between the two intervention arms. While we hypothesize that the dialogue-based webinar intervention (Arm 1) will be superior to the social media website intervention (Arm 2), a finding of superiority, inferiority, or no distinguishable difference will be a valuable finding.

For Aim 2, hypothesis 2.1, our mediation analyses seek to identify the relationship between the interventions, mediator variables, and primary and secondary outcomes. We are interested in whether interventions operate through the mediator rather than directly affecting the outcome. If the results for Aim 1 are non-significant, we will determine whether it is a null effect of the intervention on the mediator or a null effect of the mediator on the outcome. We will determine mediation strength and mechanism generalizability by comparing effects across subgroups.

For Aim 2, hypothesis 2.2, our exploratory moderation analyses (also referred to as heterogeneity of treatment effects (HTE) analyses) seek to understand whether certain participant characteristics and beliefs influence the relationship between the interventions and vaccine confidence, as well as other secondary outcomes. We will explore moderators including (but not limited to) vaccination status, religious beliefs, age, race, ethnicity, perceived influence of others, and personal experiences with COVID-19.

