P-values ≥ 0.0001 will be reported to 4 decimal places; p-values less than 0.0001 will be reported as " <0.0001 ". The mean, standard deviation, and any other statistics other than quantiles, will be reported to one decimal place greater than the original data. Quantiles, such as median, minimum, or maximum will use the same number of decimal places as the original data. Estimated parameters, not on the same scale as raw observations (e.g. regression coefficients) will be reported to 3 significant figures.

Adherence to interventions

Analysis of both intention-to-treat (ITT) and as-treated populations will be performed. All participants who are randomized to a trial arm will be included in the ITT analyses. Participants who adhere to major engagement criteria for their primary intervention will be included in the as-treated analyses.

Analysis methodology

Aim 1

To compare the impact of two interventions delivered online: 1) a dialogue-based webinar (webinar) using the existing COVID-19 Option Grid conversation aid and, 2) an interactive and, dynamic, and multi-component social media web application (social media website), compared to enhanced usual practice (link to Centers for Disease Control (CDC) vaccine website), on COVID-19 vaccine confidence (primary outcome), and other secondary outcomes among LTCWs. We hypothesize that each intervention will be superior to enhanced usual practice at increasing vaccine confidence (*Hypothesis 1.1*) and that the dialogue-based webinar intervention will be superior to the social media arm at increasing vaccine confidence (*Hypothesis 1.2*).

Corresponding analyses

Primary outcome

The primary outcome is the binary classifier of vaccine confidence derived from the three-item Vaccine Confidence Index (VCI), evaluated at 3 weeks post-randomization, which will be analyzed by randomization arm. The determined binary predictors of intervention outcomes will be compared using two-proportion z-tests to identify significant differences between each intervention and enhanced usual practice (Arm 1 vs Arm 3 & Arm 2 vs Arm 3 - superiority analyses) and between the intervention arms (Arm 1 vs Arm 2 - two-tailed equivalency analysis).

Secondary outcomes

- *Change from baseline in COVID-19 Vaccine Confidence.* Analysis of change from

baseline will be based on a binary classifier whether the average score increases (1) or does not increase (2) at T1, T2, and T3 versus baseline.

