- *Feeling informed about the COVID-19 vaccines*. The degree to which participants' feel informed about the COVID-19 vaccines (have enough information and understand that information) will be evaluated using a continuous variable, calculated as the mean scale

score across two items ((1) having enough information, (2) understanding the information) for each participant. The mean of all mean scores will be compared across trial arms with two-sample unpaired t-tests.

- *Identification of COVID-19 vaccine information and misinformation.* Subjects' identification of COVID-19 vaccine information and misinformation will be scored on a scale of zero to four and treated as a continuous linear variable. Results will be compared across trial arms with two sample unpaired t-tests.
- *Trust in COVID-19 information from different sources.* Subjects' trust in COVID-19 information from different sources will be evaluated using a continuous variable, calculated as the mean scale score across three items for each participant. The mean of all mean scores will be compared across trial arms with two-sample unpaired t-tests.
- *Change from baseline in secondary outcomes.* Change from baseline will be scored as a binary variable with an increased value scored as one and a no change or decreased value scored as zero. For each evaluation after baseline, each arm will be compared using two-proportion z-tests. For vaccine and booster intent questions, where the intent question is not repeated if the participant indicates an increase in vaccination status, intent will be imputed from uptake. To be clear, an individual who is unvaccinated at T0, then returns at T1 and indicates that he or she is now vaccinated, will be presented with the vaccine intent question at T0 but not at T1. Because the individual is now vaccinated, asking about vaccine intent at T1 would be confusing. For analyzing change in vaccine intent, the individual whose vaccine status increases would be considered to have positive intent at T1. A similar approach will be used for booster intent.
- *As treated analysis of primary and secondary outcomes.* Primary and secondary outcome analyses will be repeated, limited to the as treated samples.

Aim 2

To determine if LTCWs' characteristics and other factors mediate and moderate the interventions' impact on vaccine confidence and other secondary outcomes.

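### The secondary as-treated analysis compares engagers across arms with different access steps, so it is not protected by randomisation and can be biased in either direction

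*Combined protocol and SAP*

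**What the plan says.** Section 4.8.2 runs all Aim 1 and Aim 2 analyses by intention-to-treat and also on an "as-treated basis (i.e. whether they engaged with their assigned intervention or control"). Section 4.5.2 describes the same set as people exposed to their primary intervention. Appendix B (Adherence to interventions) gives the inclusion rule: "Participants who adhere to major engagement criteria for their primary intervention will be included in the as-treated analyses". The criteria themselves are not defined for any arm in the text available for review.

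Appendix B then specifies the method: "Primary and secondary outcome analyses will be repeated, limited to the as treated samples". For vaccine confidence at three weeks, the repeated analysis is the one in which arms are "compared using two-proportion z-tests to identify significant differences between each intervention and enhanced usual practice". The scale-score secondary outcomes use unpaired t-tests. No baseline adjustment, weighting or complier method is added for the subset.

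Access differs by arm. Under section 4.7.3, Arm 1 participants go to a separate survey "where they can sign up for one of several pre-scheduled webinar sessions", and section 4.4.3 has the live session lasting up to an hour. Arm 2 participants are redirected to the website and must create a log-in. Arm 3 participants "will be automatically redirected to a specific page(s) on the CDC website". Section 4.4.2 explains that the refreshers were developed "In response to low intervention exposure in one trial arm (webinar attendance) experienced in the first several weeks of data collection".

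On status, Appendix B analyses the primary outcome by randomised arm. Its Table 1 lists as-treated results among the secondary outcomes. Its Multiple testing section reads secondary results, naming as-treated, for direction and without a threshold.

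**The concern.** The set keeps each participant in the assigned arm and drops those who did not engage, so it is closer to a per-protocol set than to a true as-treated one. Each arm is filtered on a different behaviour after randomisation. Signing up for and sitting through a scheduled live session selects people differently from creating a log-in or following a redirect. If whatever drives attendance is related to vaccine confidence, the engagers in the three arms differ before any intervention effect, and an unadjusted test counts that difference as treatment effect.

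This matters most if the intention-to-treat result is flat because few people attended. The plan does not say which basis prevails if the two disagree. A systematic difference in the engager subset could then be read as efficacy among those exposed, or could hide a real benefit. The change-from-baseline outcomes do not restore comparability, because attenders may also differ in openness to change.

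**Working it through.** **The yardstick.** Section 4.6 states 80% power for an 8-point difference with 600 per arm, two-sided 0.05. The control rate is not given. At 40% vs 48% (pooled rate 44%):

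- SE under no difference = √(2 × 0.44 × 0.56 / 600) = 0.02866
- SE under the alternative = √((0.40 × 0.60 + 0.48 × 0.52) / 600) = 0.02857
- Power = Φ((0.08 − 1.96 × 0.02866) / 0.02857) = Φ(0.834) = 0.798

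Across control rates of 0.33 to 0.59 the power is 0.79 to 0.82. The stated figure reproduces, so 8 points is a fair scale for judging bias. The documents give no figure for the as-treated analysis itself.

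**Bias formula.** Suppose there is no treatment effect, so the proportion confident is p in every arm. Let a be the proportion engaged in an arm and d the confidence gap, engagers minus non-engagers. Since p = a·p(engaged) + (1 − a)·p(not engaged), it follows that p(engaged) = p + (1 − a)d. With the same d in both arms, the spurious Arm 1 minus Arm 3 difference is

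(1 − a₁)d − (1 − a₃)d = (a₃ − a₁)d.

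Neither p nor the sample size enters. Attrition unrelated to engagement and outcome leaves the bias unchanged.

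**Inputs.** All are assumptions, because the documents state none: a₁ = 30–50%, d = 10 points, a₃ = 100%, 80% or 60%.

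| Arm 3 counted as engaged | a₁ = 50% | a₁ = 30% |
|---|---|---|
| 100% | (1.0 − 0.5) × 10 = 5 | (1.0 − 0.3) × 10 = 7 |
| 80% | (0.8 − 0.5) × 10 = 3 | (0.8 − 0.3) × 10 = 5 |
| 60% | (0.6 − 0.5) × 10 = 1 | (0.6 − 0.3) × 10 = 3 |

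A 5-point gap halves every entry. A gap of −10 points gives the same sizes against the webinar. With equal engagement the bias is zero.

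**Second model.** Let engagement and confidence follow a bivariate normal liability with correlation ρ, 40% confident in every arm, no effect, and engagement of 30% (webinar) and 90% (CDC). The difference among engagers is +3.8 points at ρ = 0.1, +7.7 at 0.2, +11.7 at 0.3 and −3.7 at −0.1. With 80% engagement in every arm it is 0. Analysed by randomised arm, the same scenarios give 0.

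**What a complier-average estimate would cost.** Without cross-arm access, the estimate is the intention-to-treat difference divided by the proportion exposed. Before covariate adjustment, and treating that proportion as known, the interval widens by 1/0.5 = 2 to 1/0.3 = 3.3 times relative to intention-to-treat.

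**The case against.** The strongest reply is about status. The primary outcome is analysed by randomised arm, as-treated is secondary, and Appendix B (Methods to minimize bias) adds an intention-to-treat analysis of the unmodified data. All of that stands and limits the weight of the point. It does not remove it. Section 4.8.2 places the two bases side by side without saying which governs, and reading results for direction gives no protection against a systematic shift.

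Four stronger readings are tempting and are not supported:

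- *That the analysis has an inflated false-positive rate at the 2.15 SE cut-off.* Appendix B reserves that cut-off for the primary superiority tests and sets no threshold for as-treated results. Only the bias in points is relevant.
- *That nearly all of Arm 3 will count as engaged.* A redirect is not engagement. Section 4.5.2 plans to measure use of the control material and to ask why people did not take it up, so the plan expects some non-engagement. The table shows how much this matters.
- *That the bias must favour the webinar.* The most worried workers may be the ones who come to a question-and-answer session.
- *That attendance stayed low throughout.* Section 4.4.2 refers only to the first several weeks and gives no rate.

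A complier-average estimate is also not free of assumptions. Section 4.1.5 says "Access to interventions will be restricted to those assigned to each intervention arm, via the provision of unique access links", but the same section audits for inadvertent contamination, so zero cross-arm exposure should not be taken for granted. The exclusion assumption is strained in both directions. Arm 1 participants are sent the Option Grid link before the webinar (section 4.4.3), so non-attenders may still be exposed to part of the content. Only Arm 3 is redirected to the CDC page.

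**Conclusion.** The point holds for a secondary analysis. As written, the as-treated contrast filters each arm on a different post-randomisation behaviour and applies unadjusted tests, so it can be biased in either direction.

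Under the stated assumptions (no true effect, 30–50% webinar attendance, a 10-point engager gap common to both arms), the spurious difference is 1–7 points depending on Arm 3 engagement, against a design effect of 8. These figures illustrate what selection alone can do. They do not predict this trial, because attendance, gap and control rate are not in the documents.

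A reader might infer that the sponsor intends to rest a claim of webinar efficacy on this subset. Nothing in the documents says so. The gap is that the plan neither rules it out nor fixes the engagement criteria in the text available. The primary intention-to-treat comparison is not affected by this point.

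**What to change.** 1. In section 4.8.2 and Appendix B (Adherence to interventions; Secondary outcomes), state that intention-to-treat governs conclusions. Label the engager-subset results descriptive and non-randomised, adjust them for the T0 Vaccine Confidence Index, and apply this to Arm 1 vs Arm 2 as well. Fix the engagement criteria for each arm before any outcome analysis.
2. For Arm 1 vs 3 and Arm 2 vs 3 at T1, estimate efficacy among those exposed with a complier-average effect. Use randomised arm as the instrument, adjust for T0 confidence, and take exposure from Zoom attendance and website log-ins. Refreshers go out one week before the T2 invitation, so they do not affect T1.
3. Code the cross-arm access found by the section 4.1.5 audit as exposure received, rather than assuming none. Report the exclusion assumption as a limitation, with a sensitivity analysis covering the pre-webinar Option Grid link in Arm 1 and the CDC redirect in Arm 3 only.
4. At T2 and T3, count refresher use as exposure, and note that webinar-refresher use may rest on self-report (section 4.5.2).

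The cost is SAP wording and modest extra analysis, since the activity data and baseline confidence are already collected. The downside is wider intervals and reliance on the exclusion assumption. Arm 1 vs Arm 2 has no complier estimate under this fix and rests on intention-to-treat.

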4.3 Participants

4.3.1 Randomized Controlled Trial (Aims 1 and 2)

Eligible participants will include vaccinated and unvaccinated LTCWs who self-identify as: 1) being 18 years and older, 2) living in the United States, 3) having worked in a long-term care setting in the past two years, 4) able to verify their LTCW status, 5) not currently pregnant or breastfeeding, and 6) able to read, write, and understand English, and 7) being at least somewhat worried about the COVID-19 vaccines and/or not having received any COVID-19 booster vaccine (see Table 2).

Eligible LTC settings will include nursing homes, skilled nursing facilities, assisted living facilities, home health care, hospice care, and retirement communities. The two-year timeframe will avoid excluding those who are currently unemployed, and will approximately cover the duration of time since the COVID-19 pandemic began. To ensure a high proportion of study participants represent our low confidence target group, we will use two criteria – worry about the vaccines and booster uptake – to screen participants for eligibility. These criteria are based on a preliminary analysis of panel survey data, which found associations between booster intent, worry about the vaccines, and vaccine confidence.

Table 2. Screening questions and eligibility criteria

Question	Eligible Response(s)	Ineligible Response(s)
Can you read, write, and understand English? (adapted from ³⁶)	Yes	No
How old are you?	18-19 years; 20-24 years; 25-29 years; 30-34 years; 35-39 years; 40-44 years; 45-49 years; 50-54 years; 55-59 years; 60-64 years; 65 years or older	Less than 18
Do you live in the United States?	Yes	No
This study is for long-term care workers. We must be sure that everyone who joins is giving us the correct information about who they are. We also need to be sure that everyone has worked in a long-term care setting. It is important to our study results. The information that you provide in this survey will help us confirm your identity and that you are a long-term care worker. We will never contact your employer about your participation in the study.	N/A	N/A
Have you worked in a long-term care setting in the past 2 years? This includes nursing homes, skilled nursing facilities, assisted living facilities, home health care, hospice care, and retirement communities.	Yes	No

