We hypothesize that increased perceptions of feeling informed about the vaccines, identification of vaccine information and misinformation, and trust in vaccine information provided by different sources will explain (mediate) the relationship between the interventions and vaccine confidence, as well as other secondary outcomes (*Hypothesis 2.1*).

We will also conduct exploratory heterogeneity of treatment effects (HTE) analyses to identify whether certain participant characteristics and beliefs moderate the relationships among each of the interventions and vaccine confidence, as well as other secondary outcomes. Variables to be explored will include, but are not limited to, baseline vaccination status, religious beliefs, perceived influence of others, age, race, ethnicity and personal experiences with COVID-19.

Corresponding analyses

Mediation analysis

We hypothesize that the relationship between participants' assigned trial arm and primary and secondary outcomes will be mediated by the effects of feeling informed, trust in vaccine information, and beliefs about vaccines (measured through questions to determine each participant's ability to correctly classify vaccine information and misinformation). Responses for these three variables will be evaluated at each time point versus outcomes by randomization arm to identify differences by arm using the Kruskal-Wallis test. Significant relationships will be explored for mediation effects in the primary and secondary outcome analyses using the method of Barron and Kenny [2]. If this results in a significant improvement in model prediction, hypothesis 2.1 will be supported.

Heterogeneity of treatment effects/Moderation analysis

To understand how the relationship between study interventions and outcomes are moderated by participant characteristics including age, gender, location (level of regional analysis selected for appropriate granularity), educational attainment, race and ethnicity, health insurance status, health literacy, religiosity, LTCW role, duration of experience in long-term care, extent influenced by others regarding COVID-19 vaccination, personal experiences with COVID-19 and the vaccines, and baseline vaccination status, we will evaluate the primary and secondary outcomes using linear and logistic regression in a mixed-effects model.

Exploratory analyses

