Change from baseline in COVID-19 Vaccine Confidence. Looking deeper at the change in vaccine confidence, analyses will consider (a) the proportion of positive (agree and strongly agree) responses in the VCI, (b) positive responses in each of the three VCI questions. Significant correlates with demographic, contextual, and study variables will be evaluated.

External contextual factors. Outside of the study surveys and throughout the trial, we will monitor external factors that may impact participants' views and actions towards the COVID-19 vaccines. This may include monitoring policy and mandate changes for LTCWs and changes in the nature of the pandemic, among other things.

Additional analyses. Any unvalidated thresholds utilized in the primary or secondary analyses will be evaluated for sensitivity to the choice of threshold in ROC analyses. Nonlinear higher-dimensional effects and interactions among variables will be identified by identifying positive or negative outcomes grouped around specific baseline characteristics that are highly unlikely to result from random chance.

Duplicate and missing data

Participants must complete a baseline (T0) survey to be considered enrolled in the study. In the event of duplicate complete T0 submissions, the first complete survey will be used. For participants who complete duplicate follow-up surveys (T1, T2 or T3), the first complete survey

will also be used. In order to be included in primary and secondary outcome analyses, participants must have valid primary outcome data at both T0 and T1.

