The primary outcome involves three separate tests, one a two-tailed equivalence test and two one-tailed superiority tests. In order to achieve a family-wise error rate less than 0.050, the Bonferroni method was employed to set a p-value threshold at 0.016 for each of the three primary outcome analyses. For each comparison, mean-value separation will be considered significant based on a 98.4% confidence interval, which translates to +/- 2.45 times the standard

error for the sample mean for the equivalence test and greater than 2.15 times the standard error for the superiority analyses.

Based on the high number of secondary outcome analyses (cross-sectional T1; change from baseline; ITT; as-treated), results data for these outcomes will be viewed in more aggregate form as trending in one direction or not, rather than adopting a specific Bonferroni-corrected p-value threshold.

References

1. B. Rocks, Interval Estimation for the “Net Promoter Score.” *Am. Stat.* 70, 365–372 (2016).
2. R. M. Baron, D. A. Kenny, The moderator–mediator variable distinction in social psychological research: Conceptual, strategic, and statistical considerations. *J. Pers. Soc. Psychol.* 51, 1173–1182 (1986).
3. T.E. Raghunathan, J.M. Lepkowski, J. Van Hoewyk, P. Solenberger, et al. A multivariate technique for multiply imputing missing values using a sequence of regression models. *Surv. Methodol.* 27, 85–96 (2001).

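### The primary z-test ignores the baseline VCI that every analysed participant must have: valid, but less precise than it could be for free

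*Combined protocol and SAP*

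**What the plan says.** Appendix B (Primary outcome) defines the endpoint: "The primary outcome is the binary classifier of vaccine confidence derived from the three-item Vaccine Confidence Index (VCI), evaluated at 3 weeks post-randomization". The arms "will be compared using two-proportion z-tests to identify significant differences between each intervention and enhanced usual practice", and Arm 1 is compared with Arm 2 by a two-tailed test. No covariate is named.

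Under Duplicate and missing data, entry to the primary and secondary analyses is conditional: "participants must have valid primary outcome data at both T0 and T1". Sections 4.7.2 and 4.7.3 place the T0 outcome questions before the arm is generated at the end of that survey, so T0 VCI is a true pre-randomization measurement. On allocation, section 4.7.3 says "A 1:1:1 allocation ratio will be used" and describes no stratification.

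Baseline data are used elsewhere: for change-from-baseline outcomes, exploratory analyses and imputation. For moderation, "we will evaluate the primary and secondary outcomes using linear and logistic regression in a mixed-effects model"; baseline VCI is not among the characteristics named in that paragraph, and this model does not replace the primary test. Multiple testing in Appendix B uses Bonferroni to "set a p-value threshold at 0.016 for each of the three primary outcome analyses".

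**The concern.** A participant's confidence three weeks earlier should be a good predictor of confidence at T1. Leaving it out of both the randomization and the analysis means that chance differences between arms in baseline confidence stay in the error of the comparison. The standard error of all three primary contrasts is then larger than the trial's own data require, and a true 8-point difference is more likely to be missed. No bias is alleged.

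A smaller related point concerns the secondary VCI change outcome. It records only whether the average score rose. A fall counts the same as no change, and a participant already at the top of the scale can never count as improved.

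**Working it through.** **Inputs from the documents.** 600 per arm and an 8-point difference, or a 10-point difference after 40% attrition, which leaves 600 × 0.6 = 360 per arm (section 4.6). Per-test threshold 0.016, with a one-tailed multiplier of 2.15 (Appendix B, Multiple testing). For the two-tailed test I use 2.409, the normal quantile for 0.016; the plan's own multiplier of 2.45 lowers the two-tailed power figures below by 2 points or less.

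**Assumed inputs.** The control rate is not given, so I show 46%, 30% and 20%. The correlation r between the T1 binary outcome and the baseline predictor is not given either; I show 0.1 to 0.56.

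**Formulas.** SE = √[(p₁q₁ + p₂q₂)/n] × √(1 − r²). Power = Φ(d/SE − z). Equivalent sample = n/(1 − r²).

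**The plan's own figure.** At 46% v 54%, SE = √[(0.2484 + 0.2484)/600] = 2.88 points. At two-sided 0.05, power = Φ(8/2.877 − 1.96) = 79.4%, which agrees with the 80% in section 4.6.

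**At the threshold actually used.** Unadjusted, one-tailed: Φ(2.780 − 2.15) = 73.6%. Two-tailed: Φ(2.780 − 2.409) = 64.5%. With r = 0.5, SE = 2.877 × 0.866 = 2.49, and power is Φ(3.211 − 2.15) = 85.5% and Φ(3.211 − 2.409) = 78.9%.

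Power in %, one-tailed/two-tailed, 600 per arm, 8 points, threshold 0.016:

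| r | Equivalent n per arm | Control 46% | Control 30% | Control 20% |
|---|---|---|---|---|
| 0 (as planned) | 600 | 74/65 | 78/70 | 87/80 |
| 0.1 | 606 | 74/65 | 79/71 | 87/81 |
| 0.2 | 625 | 75/67 | 80/72 | 88/82 |
| 0.3 | 659 | 78/69 | 82/75 | 90/84 |
| 0.4 | 714 | 81/73 | 85/79 | 92/87 |
| 0.5 | 800 | 86/79 | 89/84 | 95/91 |
| 0.56 | 874 | 89/83 | 92/87 | 96/94 |

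With 360 per arm and 10 points, at r = 0, 0.3 and 0.5: 71/61, 75/66 and 83/76 at a 46% control rate; 83/76, 87/81 and 93/88 at 20%.

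**Is the range of r reasonable?** A simulation generated three 1–5 items at T0 and T1, scored confidence as all three items at 4 or above, and fitted a logistic model on arm and T0 mean score (600 per arm, 8-point effect, 3,000 trials per setting). At a 46% control rate:

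| T0–T1 mean-score correlation | SE unadjusted → adjusted (points) | Effective r |
|---|---|---|
| 0.42 | 2.88 → 2.72 | 0.33 |
| 0.59 | 2.89 → 2.53 | 0.48 |
| 0.72 | 2.80 → 2.29 | 0.58 |

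At a 20% control rate the effective r was 0.30, 0.47 and 0.57 for similar correlations. Mean effects with and without adjustment agreed within 0.05 points. A separate simulation, standardizing over binary baseline status at 360 per arm under no effect, gave rejection rates of 5.2–5.5% adjusted and 4.6–5.5% unadjusted at a nominal 5%.

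**The case against.** An unadjusted comparison of proportions is conventional, and nothing in the plan is contradictory or wrong on this point. That stands: this is advice on efficiency.

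The gain depends on a correlation the documents do not give. Eligibility is built "To ensure a high proportion of study participants represent our low confidence target group", and that selection could narrow the spread of baseline scores and lower r. At r = 0.2 the gain is only about 1 to 2 points of power, and at r = 0.1 about half a point. This stands as a limit on the size. It is also why the baseline mean score is a better covariate than the baseline yes/no status, which may have few positives.

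Much of the distance between 80% and 74/65% comes from testing at 0.016 after sizing at 0.05, not from the choice of test. That is correct and is a separate matter; adjustment helps at either level.

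The z-test is called valid here only in respect of covariates. Delivery of Arm 1 in groups of up to 20 may correlate outcomes. As an assumption, an intracluster correlation of 0.02 in that arm gives a design effect of 1 + 19 × 0.02 = 1.38 and raises the SE from 2.88 to 3.14 points. Restricting the analysis to responders at T0 and T1 raises its own questions. Neither is cured or worsened by ignoring baseline VCI.

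Finally, section 4.4.2 shows that data collection has begun, so the change is a formal amendment under section 5.2. That adds procedure but is no reason against it.

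**Conclusion.** The concern holds. The primary analysis leaves unused a pre-randomization covariate that the plan requires from every analysed participant. The consequence is lost precision, not bias. For r between 0.3 and 0.5, adjustment is worth roughly 60 to 200 extra participants per arm whatever the control rate. In power, r = 0.3 brings about 3 to 5 points. At r = 0.5 the gain is about 12 to 14 points with a 46% control rate, and less at lower rates because unadjusted power is already higher. These figures assume independent observations and rest on assumed values of r and the control rate. The amendment is worth making because the cost is small, but the trial is interpretable without it. The coarse change classifier is a minor, accurate side point.

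**What to change.** Before any outcome data are analysed, amend Appendix B so that the primary analysis is a logistic regression of T1 VCI confidence on arm, with T0 VCI mean score and baseline vaccination status as covariates. From it, report the standardized (marginal) risk difference with a robust standard error for each of the three comparisons, at the significance levels already set under Multiple testing. The estimand stays a difference in proportions, matching section 4.6. Keep the two-proportion z-test as an unadjusted supporting analysis. The calculations above credit only the T0 score; any gain from vaccination status has not been quantified.

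For the secondary VCI change outcome, add or substitute an analysis of covariance of the mean VCI score at T1, T2 and T3 on the T0 score.

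The cost is a few lines of SAP text, the amendment reporting described in section 5.2, and a matching update to the independent replication by the DSMB statistician. No new data are needed.
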